7.1.3. Sensitivity and Supportive Analysis Methods

- The primary endpoint will be repeatedly analysed in the following subgroups, using the same method used in primary analysis method:
 - ✓ Type of baseline controller (inhaled corticosteroids [ICS] alone vs. ICS/long-acting β 2 agonist [LABA])
 - ✓ Gender (male vs. female)
 - ✓ Age (<50 years old vs. \geq 50 years old)

For subgroup analyses, the model will include all the covariates used in the primary analysis model except for the subgroup variable itself. Adjusted odds ratios and their 95% confidence intervals will be presented by a forest plot. These analyses will be performed for the ITT and PP populations.

- A supportive analysis of the primary endpoint will be performed using Generalised Estimating Equations (GEEs) if the model can converge.

All non-missing data from visits with scheduled ACT assessments (Weeks 4, 8, 12, 16, 20 and 24) will be included and an unstructured working correlation matrix will be implemented. The model will include terms for treatment, baseline ACT total score, baseline ACT total score squared, age, gender, visit and treatment-by-visit interaction. The number and percentage of subjects with a response within each treatment group will be presented by visit, together with the adjusted odds ratios, 2-sided 95% confidence intervals, and associated p-values between ACT guided treatment and usual care. The adjusted odds ratios and 95% confidence intervals will be presented by a forest plot.

The example SAS codes are as below:

```
proc genmod data=input_data descending;
class rndgrp gender visit subjid/ ref=first param=ref;
model response=rndgrp actbl actblsq blcontrol age gender visit
rndgrp*visit/dist=bin;
repeated subject=subjid /within=visit type=un corrw;
estimate "Treatment effect at Visit 1" rndgrp 1 visit 0 0 0 0 0
rndgrp*visit 0 0 0 0 0/exp;
estimate "Treatment effect at Visit 2" rndgrp 1 visit 0 0 0 0 0
rndgrp*visit 1 0 0 0 0/exp;
estimate "Treatment effect at Visit 3" rndgrp 1 visit 0 0 0 0 0
rndgrp*visit 0 1 0 0 0/exp;
estimate "Treatment effect at Visit 4" rndgrp 1 visit 0 0 0 0 0
rndgrp*visit 0 0 1 0 0/exp;
estimate "Treatment effect at Visit 5" rndgrp 1 visit 0 0 0 0 0
rndgrp*visit 0 0 0 1 0/exp;
estimate "Treatment effect at Visit 6" rndgrp 1 visit 0 0 0 0 0
rndgrp*visit 0 0 0 0 1/exp;
run;
```

where input_data is the name of the input dataset and response is the response variable. In terms of the covariates rndgrp, actbl, actblsq, blcontrol, gender, age and visit are variables for randomised treatment code, baseline ACT total score, baseline ACT total score squared, type of baseline controller, gender, age and visit number, respectively. For repeated measures, visit is variable for visit number and subjid is variable for subject's ID.

This analysis will be performed for the ITT and PP populations.

- Percentage of subjects who have an ACT total score ≥ 20 and an improvement of more than 3 points in ACT total score.

The following endpoints will be analysed as sensitivity analyses.

- ✓ Percentage of subjects who have an ACT total score ≥ 20 and an improvement of more than 3 points in ACT total score at Week 12. Subjects with missing data at Week 12 will be set as non-responders.
- ✓ Percentage of subjects who have an ACT total score ≥ 20 and an improvement of more than 3 points in ACT total score at Week 24. Subjects with missing data at Week 24 will be set as non-responders.
- ✓ Percentage of subjects who have an ACT total score ≥ 20 and an improvement of more than 3 points in ACT total score at Weeks 16 and 20 and 24. Subjects with missing data at Weeks 16, 20 or 24 will be set as non-responders.

These endpoints will be analysed using the same model as defined for primary endpoint (GLMM). A supportive analysis will be conducted to analysis the percentage of subjects who have an ACT total score ≥ 20 and an improvement of more than 3 points in ACT total score, using the same GEEs method as mentioned above. All non-missing data from visits with scheduled ACT assessments (Weeks 4, 8, 12, 16, 20 and 24) will be used.

These analyses will be performed for the ITT and PP populations.

- Change from baseline in ACT total score in post-baseline visits.

A Mixed Model Repeated Measures (MMRM) will be used with covariates of treatment, baseline ACT total score, centre, type of baseline controller (ICS alone vs. ICS/LABA), gender, age, visit, treatment-by-visit interaction and treatment-by-baseline ACT total score, with centre as a random effect. The least squares (LS) mean and LS mean change from baseline for each treatment and the estimated LS mean change from baseline treatment difference will be presented at each visit together with the 95% confidence interval for the mean difference and P-value.

The example SAS codes are as below:

```
proc mixed data=input_data;
class invsite rndgrp visit subjid blcontrol gender;
model actchbl=rndgrp actbl blcontrol gender age visit rndgrp*visit
rndgrp*actbl/ ddfm =kr;
random intercept/subject= invsite;
repeated visit / subject=subjid type=un;
lsmeans rndgrp*visit / cl diff e;
ods output lsmeans=lsmeans;
ods output diffs=diffs;
run;
quit;
```

where input_data is the name of the input dataset and actchbl is change from baseline in ACT score. In terms of the covariates rndgrp, actbl, blcontrol, gender, age and visit are variables for randomised treatment code, baseline ACT total score, type of baseline controller, gender, age and visit number, respectively. For random effect, invsite is variable for centre. For repeated measures, visit is variable for visit number and subjid is variable for subject's ID.

This analysis will be performed for the ITT and PP populations.

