9.4.1. Primary Analyses

The primary endpoints will be analyzed using logistic regression. The statistical model on which the inference will be based will include terms for treatment, centre, type of baseline controller (ICS alone vs. ICS/LABA), gender and age. Centre, as the unit of randomization, will be treated as a random effect. The results of the primary analyses will be presented as point estimates, 95% confidence intervals and associated p-values for the adjusted mean differences between ACT guided treatment and usual care.

Analyses of the primary endpoints will be performed on the ITT population and the PP population; the ITT population is considered primary.

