9.4.3. Other Analyses

Asthma exacerbation rate will be analyzed using logistic regression as described for the primary endpoints.

Interactions between treatment and each of the covariates will be investigated in turn, with all main effects in the model regardless of their statistical significance. Any

interaction terms found to be statistically significant will be explored and if necessary results will be reported for each level of the covariate. Investigation of interactions will be confined to the primary endpoints. The effect of interactions (e.g., treatment by centre) will be assessed at the 10% level of significance.

Adverse events

The number (%) of subjects in each treatment group with treatment emergent AEs will be produced. Counts and percentages will also be presented of subjects with serious adverse events (SAEs), AEs leading to withdrawal, AEs by severity and AEs by relationship to study drug.

Other safety measures

Reason for withdrawal will be summarised.

Summary statistics for vital signs evaluations at each visit will be presented by treatment group. In addition, summary statistics for change from baseline for vital signs evaluations will be presented by treatment group.

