2. SUMMARY OF KEY PROTOCOL INFORMATION

2.1. Changes to the Protocol Defined Statistical Analysis Plan

There were no changes or deviations to the originally planned statistical analysis specified in the protocol, dated 27-Jun-2016. Some sensitivity and supportive analyses are added in the primary efficacy analysis in this RAP (See details in Section 7.1.3).

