7. EFFICACY ANALYSES

All hypothesis tests and confidence intervals will be two-sided. All efficacy measures over the course of the study will be presented and summarised. Continuous data will be summarised by means, standard deviations (SD), medians, minimum and maximum; categorical data will be summarised by counts and percentages.

All outcomes will be pertained to the individual participant's level and the analysis model will be adjusted for the effect of centre (cluster).

Unless otherwise specified, endpoints / variables defined in Section [7.1](#) and Section [7.2](#) will be summarised using descriptive statistics, graphically presented (where appropriate) and listed.

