7.3. Exploratory Efficacy Analyses

Moderate/severe asthma exacerbations will be summarized, including number of subjects with moderate/severe exacerbations, number of moderate/severe exacerbations and characteristics of moderate/severe exacerbations. Exacerbations separated by less than 7 days will be treated as a continuation of the same exacerbation

The moderate/severe exacerbation rate will be analyzed using a generalized linear model, assuming the number of exacerbations has a negative binomial probability distribution and that its mean is related to covariate factors with a 'log link' function. The logarithm of time (year) on study will be used as an offset variable. All moderate/severe

exacerbations observed during the study, with the onset date of event from date of baseline visit to the end of study visit date or early withdrawal (from study) visit date, will be included in the analysis. Missing data due to early withdrawal from the study will not be imputed. The model will include covariates for treatment, baseline ACT total score, type of baseline controller (ICS alone vs. ICS/LABA), gender and age. The annual moderate/severe exacerbation rates and 95% confidence interval for each treatment will be presented. The rate ratio and 95% confidence interval, percent reduction in rate and 95% confidence interval and P value will also be presented.

The example SAS codes are as below:

```
proc genmod data= input_data;  
  class rndgrp blcontrol gender;  
  model no_exac = rndgrp actbl blcontrol gender age / dist=negbin  
link=log offset=logtime wald type3;  
  lsmeans rndgrp / cl diff OM exp;  
run;
```

where input_data is the name of the input dataset and no_exac is the number of moderate/severe asthma exacerbations per subject during the study. In terms of the covariates rndgrp, actbl, blcontrol, gender and age are variables for randomised treatment code, baseline ACT total score, type of baseline controller, gender and age respectively. For offset, logtime is logarithm of time (year) on study.

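### The supportive GEE analyses and the exacerbation count model leave out centre, the unit of randomisation; at the plan's ICC of 0.01 a nominal 5% GEE test has about 9% type I error

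*SAP*

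**What the plan says.** The general rule, in SAP 7, is that outcomes are analysed at patient level and that the "analysis model will be adjusted for the effect of centre (cluster"). Protocol 9.4 says the same. The primary GLMM (SAP 7.1.2), the GLMMs for the AND definition of response, and the MMRM for change in ACT (SAP 7.1.3) all follow it with a random intercept for the centre variable `invsite`.

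Two sets of models do not follow it.

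- **Supportive GEE, SAP 7.1.3.** The text reads: "The model will include terms for treatment, baseline ACT total score, baseline ACT total score squared, age, gender, visit and treatment-by-visit interaction". In the code, `invsite` appears in no CLASS, MODEL or REPEATED statement, and the only clustering unit is the patient: "repeated subject=subjid /within=visit type=un corrw". The AND definition of response is then analysed "using the same GEEs method as mentioned above". Both GEEs are planned for the ITT and PP populations. The method reports odds ratios, confidence intervals and p-values by visit, with a forest plot.
- **Exacerbation model, SAP 7.3.** The text reads: "The model will include covariates for treatment, baseline ACT total score, type of baseline controller (ICS alone vs. ICS/LABA), gender and age". The code has no `invsite` and no RANDOM or REPEATED statement, yet a rate ratio, interval and p-value are to be reported.

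For exacerbations the protocol planned something else. Section 9.4.3 says "Asthma exacerbation rate will be analyzed using logistic regression as described for the primary endpoints", and in the primary model (9.4.1) "Centre, as the unit of randomization, will be treated as a random effect". SAP 2.1 nevertheless states: "There were no changes or deviations to the originally planned statistical analysis specified in the protocol".

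**The concern.** Arm is a property of the centre. Each arm has six centres, and all between-arm information is between-centre information. A model that allows for correlation among one patient's visits, but treats patients in the same centre as independent, leaves out the variance component that matters most for the treatment contrast. Its intervals are too narrow whenever the ICC is positive.

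The sample size was inflated for this correlation, while the two GEEs would analyse the same patients as if it were zero. They produce up to 2 response definitions × 2 populations × 6 visits = 24 by-visit comparisons, shown beside a primary analysis that does model centre. A supportive analysis is there to corroborate the primary one. This one could look sharper merely because clustering was dropped.

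The exacerbation model has the same weakness. Its change from the protocol's method is also undeclared.

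**Working it through.** **Inputs (Protocol 9.2.1).** ICC 0.01, stated for the well-control rate; response 29% v 44%; 6 centres per arm; 35 evaluable and 44 recruited patients per centre; 20% dropout; two-sided 5%; 80% power. Neither document gives an ICC, event rate or dispersion for exacerbations.

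**1. The plan's own figure.** Without clustering, and with unpooled variance, n per arm = (1.960 + 0.842)² × (0.29×0.71 + 0.44×0.56) / 0.15² = 157.8. The design effect is DE = 1 + (m − 1) × ICC = 1 + 34 × 0.01 = 1.34. Then 157.8 × 1.34 × 2 = 422.9 evaluable, or 35.2 per centre, and 422.9 / 0.8 = 528.6. This reproduces 420 and 528, so the plan's sample size does carry the full 1.34.

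**2. Error when centre is ignored.** The reported SE is 1/√DE of the true SE. The true type I error of a nominal 5% Wald test is 2 × [1 − Φ(1.96/√DE)], and coverage is its complement.

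| ICC | m = 35: DE, SE ratio, type I | m = 44: DE, SE ratio, type I |
|---|---|---|
| 0.005 (assumed) | 1.17, 0.925, 7.0% | 1.215, 0.907, 7.5% |
| **0.01 (plan)** | **1.34, 0.864, 9.0%** | **1.43, 0.836, 10.1%** |
| 0.03 (assumed) | 2.02, 0.704, 16.8% | 2.29, 0.661, 19.5% |
| 0.05 (assumed) | 2.70, 0.609, 23.3% | 3.15, 0.563, 26.9% |

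At the plan's ICC the SE is 14% too small with 35 per centre (coverage 91.0%) and 16% too small with 44 (coverage 89.9%). The 44 applies to early visits, before dropout.

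**3. Simulation of the null.**

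- Single visit, beta-binomial centres, ICC 0.01, 29% response: 9.0% (m = 35) and 10.1% (m = 44). With ICC 0 the error returns to about 5%, so the omitted centre effect is the cause.
- Six correlated visits, 12 × 35, patient-level robust SE: 8.8% on average at a 29% response rate and 9.1% at 36.5%. The within-patient correlations are assumed.
- The full GEE covariate set: about 9.2%.

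**4. Does clustering on centre cure it?** Same 12 × 35 design, ICC 0.01:

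- Centre sandwich, uncorrected, normal reference: 10.2%.
- Centre sandwich with the small-sample correction (factor 6/5 for six centres per arm) and t on 12 − 2 = 10 df: 4.8%.
- Full covariate set with the Kauermann-Carroll correction and t on 10 df: about 4.5%.

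Replacing `subjid` with `invsite` is therefore not enough. With 12 clusters the correction and the df are both needed.

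**5. Random-centre logistic model.** Single visit, maximum likelihood by quadrature, no covariates, ICC 0.01, 0.03 and 0.05:

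- Normal reference: 7.4%, 9.5%, 9.0%.
- t on 10 df: 4.1%, 6.0%, 5.9%.

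A mixed model needs between-centre df too.

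**6. Exacerbations.** The protocol has logistic regression as for the primary endpoint, hence with random centre. The SAP has negative binomial regression without centre. The direction follows from the design: intervals are too narrow for any positive ICC. The documents do not allow a size to be computed.

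**The case against.** The omission itself is not in dispute. Labelling the code as an example does not excuse it, because the written term lists leave centre out as well. The serious objections concern size and weight.

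- **Tier stratification.** Centres are randomised within hospital tier. Variance between tiers counts towards an overall ICC but is balanced across arms. Assume 6 centres per tier, 3 per arm in each, overall ICC 0.01 and 35 per centre. Type I error then falls from 9.0% to 8.0%, 7.0% or 5.9% if tier explains a quarter, a half or three quarters of the ICC. This stands as a condition on the 9%. The documents give neither the tier split nor the tier share, and the plan's own sample size applies the full design effect.
- **A smaller ICC is possible.** At 0.005 the error is 7.0% with 35 per centre; at zero there is no problem. This stands, and the table shows it.
- **The primary model is not a perfect yardstick.** SAP 7.1.2 states no df method. If its reference is close to normal, a random-centre model of that kind rejects about 7.4% at ICC 0.01, so the GEE's excess over it is nearer 1.6 points than 4. This stands.
- **SAP 2.1 does declare added supportive analyses and points to 7.1.3.** This is correct. The undeclared change concerns the exacerbation model only.
- **Little rests on these analyses.** The GEE runs only if it converges, exacerbations are exploratory, and the comparison of interest is the primary one. This limits the consequence but does not make the intervals valid.

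**Conclusion.** The concern holds. The two supportive GEEs and the exacerbation model contradict SAP 7 in both text and code. A by-visit GEE test has type I error of about 9% at 35 patients per centre and about 10% at 44. Those figures assume that the ICC of 0.01, given for the well-control rate, applies at each visit, and that tier explains none of it. A tier effect or a smaller ICC brings them down; a larger ICC takes them up quickly. For exacerbations the fault is established in direction only. The primary GLMM, the AND-definition GLMMs and the ACT MMRM are not affected by this omission. No confirmatory conclusion depends on the affected models, so this should be corrected before analysis but does not threaten the main result.

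**What to change.** Amend SAP text and code together.

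**Response by visit, one of two:**

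- **(a) Keep a marginal model.** Use GEE clustered on `invsite`, with an independence working correlation (visit no longer identifies a single record within a cluster), a small-sample-corrected sandwich variance such as Kauermann-Carroll, and a t reference on between-centre df. That is about 10, or 9 if tier is added as a covariate. This option was checked by simulation with six visits.
- **(b) Use a GLMM** with random intercepts for centre and for subject within centre, on between-centre df, and state that its odds ratio is conditional. The check above covers only a single-visit version without the subject effect, so (a) has the firmer support.

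Apply the choice to both response definitions. In the same edit, reconcile type of baseline controller, which is in the GEE code but not in its text.

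**Exacerbations.** Add a random intercept for `invsite` to the count model, with between-centre df. Pre-state a simpler fallback, such as Poisson with random centre, in case it does not converge. That is plausible because Protocol 5.3 discontinues subjects at a protocol-defined exacerbation, so counts may be mostly 0 or 1. List the change from Protocol 9.4.3 in SAP 2.1.

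**Cost.** No new data. At ICC 0.01 and 35 per centre, intervals widen by √1.34 = 1.158, about 16%, from restoring centre. With t on 10 df the factor is 1.158 × 2.228/1.960 = 1.316, about 32%. At 44 per centre the figures are about 20% and 36%. Option (a) gives up the unstructured working correlation. Option (b) changes the estimand from marginal to conditional, so point estimates shift as well.

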7.2. Secondary Efficacy Analyses

7.2.1. Endpoint / Variables

- Mean daytime symptom score over the 24-week treatment period
- Mean night-time symptom score over the 24-week treatment period
- Mean change from baseline to the end of study in FEV1
- Mean morning (AM) PEF over the 24-week treatment period
- Mean evening (PM) PEF over the 24-week treatment period
- Mean change from baseline to the end of study in AQLQ(S) score
- Time to first ACT total score ≥ 20 or improvement of more than 3 points in ACT total score over the 24-week treatment period
- Time to first ACT total score ≥ 20 and improvement of more than 3 points in ACT total score over the 24-week treatment period

7.2.2. Analysis Methods

All secondary endpoints will be confined to the ITT population. The continuous efficacy endpoints will be summarized by mean, standard deviation (SD), median, minimum and maximum according to scheduled visits. Time to event endpoint will be summarized by median time, 95% confidence interval of median time, lower and upper quantiles and range.

Continuous efficacy endpoints will be analysed using analysis of covariance (ANCOVA) and adjusted for centre as a random effect.

For mean daytime and night-time symptom score and mean morning and evening PEF, the mean values will be based on the available data on the diary card over each visit assessment period. No imputations will be performed on missing data. The mean values will be considered missing if less than 14 days are recorded in each visit assessment period. A Mixed Model Repeated Measures (MMRM) will be used with covariates of treatment, centre, type of baseline controller (ICS vs. ICS/LABA), gender and age, with the centre as a random factor. The results will be presented as LS mean (SE), 95% confidence interval for LS mean, treatment difference, 95% confidence interval for treatment difference and P-value by visit.

The example SAS codes are as below:

```
proc mixed data=input_data;
class invsite rndgrp visit subjid blcontrol gender;
model endpoint=rndgrp actbl blcontrol gender age/ ddfm =kr;
random intercept/subject= invsite;
repeated visit / subject=subjid type=un;
lsmeans rndgrp*visit / cl diff e;
ods output lsmeans=lsmeans;
ods output diffs=diffs;
run;
quit;
```

where `input_data` is the name of the input dataset and `endpoint` is the endpoint variable. In terms of the covariates `rndgrp`, `actbl`, `blcontrol`, `gender` and `age` are variables for randomised treatment code, baseline ACT total score, type of baseline controller, gender and age respectively. For random effect, `invsite` is variable for centre. For repeated measures, `visit` is variable for visit number and `subjid` is variable for subject's ID.

The AQLQ(S) contains 32 items in four domains: activity limitation (11 items), symptoms (12 items), emotional function (5 items) and environmental stimuli (4 items). The following items are included in each of the 4 domains:

- Symptoms: 6, 8, 10, 12, 14, 16, 18, 20, 22, 24, 29, 30
- Activity Limitation: 1, 2, 3, 4, 5, 11, 19, 25, 28, 31, 32
- Emotional Function: 7, 13, 15, 21, 27
- Environmental Stimuli: 9, 17, 23, 26

The response format consists of a seven-point scale where a value of 1 indicates “total impairment” and a value of 7 indicates “no impairment”. The total AQLQ(S) score is the mean of all 32 items in the questionnaire and each individual domain score is calculated as the mean of the items within that domain. Hence, the total and domain scores are also each defined on a range from 1 to 7 with higher scores indicating a higher quality of life.

For the total AQLQ(S) score, the score for a subject at any time point will only be calculated if at least 90% of the questions were answered (calculated as the mean of those non-missing questions). If fewer than 90% of the questions were answered then the mean score for that subject at that time point will be considered missing.

For each individual domain of the AQLQ(S) score, the score for a subject at any time point will only be calculated if at least 90% of the questions for that domain were answered (calculated as the mean of those non-missing questions). If fewer than 90% of the questions were answered for that domain then the mean score for that subject and domain at that time point will be considered missing.

The analysis of changing from baseline to the end of study in FEV1 and AQLQ(S) score will only include those who complete the study and change from baseline will be calculated as the difference between baseline visit and Visit 6.

For FEV1 and AQLQ(S) changing from baseline, a mixed model will be used with covariates of treatment, centre, type of baseline controller (ICS vs. ICS/LABA), gender and age, with the centre as a random factor. The results will be presented as LS mean (SE), 95% confidence interval for LS mean, treatment difference, 95% confidence interval for treatment difference

The example SAS codes are as below:

```
proc mixed data=input_data;
class invsite rndgrp blcontrol gender;
```

```

model epchbl=rndgrp actbl blcontrol gender age/ ddfm =kr;
random intercept/subject= invsite;
lsmeans rndgrp/ cl diff e;
ods output lsmeans=lsmeans;
ods output diffs=diffs;
run;
quit;

```

where `input_data` is the name of the input dataset and `epchbl` is the endpoint variable changing from baseline. In terms of the covariates `rndgrp`, `actbl`, `blcontrol`, `gender` and `age` are variables for randomised treatment code, baseline ACT total score, type of baseline controller, gender and age respectively. For random effect, `invsite` is variable for centre.

For time to event endpoint, Cox regression analysis will be performed with treatment, baseline ACT total score, centre, type of baseline controller (ICS alone vs. ICS/LABA), gender and age as the adjusted factors. The results will be presented as hazard ratio (SE), 95% confidence interval and P-value. Log-rank test and Kaplan-Meier methodology will be used to estimate median time for each treatment arm. Kaplan-Meier curves will be constructed to provide a visual description of the difference between the two treatment arms.

The example SAS codes are as below:

```

proc phreg data=input_data;
class rndgrp actbl invsite blcontrol gender;
model timetol*eventflag(0)= rndgrp actbl invsite blcontrol gender age /
risklimits ties=exact;
hazardratio rndgrp/ diff=all;
run;

proc lifetest data=input_data outsurv=survest;
time timetol*eventflag(0);
strata rndgrp;
run;

```

where `input_data` is the name of the input dataset, `timetol` is the variable for time to response and `eventflag` is the variable for sensor. In terms of the covariates `rndgrp`, `actbl`, `invsite`, `blcontrol`, `gender` and `age` are variables for randomised treatment code, baseline ACT total score, centre, type of baseline controller, gender and age respectively.

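### The diary repeated-measures model (symptom scores, PEF) is to report results by visit but contains no visit or treatment-by-visit term, and it neither requests nor in general gives the 24-week mean difference

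*SAP*

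**What the plan says.** **Endpoints.** SAP 7.2.1 defines each of the four diary endpoints as one quantity over the whole study, for example "Mean daytime symptom score over the 24-week treatment period". Night-time score, morning PEF and evening PEF are worded in the same way.

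**Response variable.** In SAP 7.2.2, "the mean values will be based on the available data on the diary card over each visit assessment period". That gives up to six values per subject (weeks 4, 8, 12, 16, 20 and 24). A period mean is set to missing if fewer than 14 days are recorded.

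**Model, in prose.** "A Mixed Model Repeated Measures (MMRM) will be used with covariates of treatment, centre, type of baseline controller (ICS vs. ICS/LABA), gender and age", with centre random.

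**Model, in code.** "model endpoint=rndgrp actbl blcontrol gender age/ ddfm =kr". Visit enters only through CLASS and "repeated visit / subject=subjid type=un".

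**Output.** The code asks for "lsmeans rndgrp*visit / cl diff e", and the prose for "95% confidence interval for treatment difference and P-value by visit".

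**Other text that bears on these endpoints.** SAP 7.2.2 first states that continuous efficacy endpoints are analysed by ANCOVA with centre random. Protocol 9.4.2 says the same and applies it explicitly to the symptom scores. Protocol 9.3.2 says that missing values are left out when symptom score and PEF over 24 weeks are calculated. SAP 2.1 declares no change to the protocol's analysis apart from additions to the primary efficacy analysis.

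**The concern.** The requested output and the fitted mean do not match. A model without visit in its mean has one expected value per arm, so it has no visit-specific difference to report. The omission is in both the prose and the code, so it cannot be put down to shortened example code.

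Two things are at stake:

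- Four of the eight secondary endpoints in the SAP have a specified model that cannot deliver its planned results. Someone will have to choose the repair, and in an open-label trial that choice is better made before database lock.
- One quick repair is to replace the LSMEANS effect with `rndgrp` alone. The program would then run, but the estimate would not in general be the 24-week mean difference that defines the endpoint.

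**Working it through.** There is no stated figure to reproduce, because this is a question of model specification.

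**1. Side by side within the SAP.**

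| Model | Visit terms in prose | Visit terms in MODEL | LSMEANS effect | Consistent? |
|---|---|---|---|---|
| ACT change from baseline (7.1.3) | visit and treatment-by-visit | "model actchbl=rndgrp actbl blcontrol gender age visit rndgrp*visit" | `rndgrp*visit` | yes |
| FEV1 and AQLQ(S) change (7.2.2) | none | none | `rndgrp` | yes |
| Diary endpoints (7.2.2) | none | none | `rndgrp*visit` | no |

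Only the diary model asks for an effect that it does not contain.

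**2. Estimability.** Two arms and six visits make 12 cell means.

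- As written, the mean has an intercept and an arm column (covariates aside): rank 1 + 1 = 2. One difference is shared by all six visits.
- With visit and treatment-by-visit added: rank 1 + 1 + 5 + 5 = 12. Every cell mean and every by-visit difference is then estimable.

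**3. What the single treatment effect estimates.** Let δ be the vector of six true visit differences and Σ the 6 × 6 covariance. With complete data, GLS estimates each arm's single mean with weights w = Σ⁻¹1 / (1′Σ⁻¹1), so the treatment effect tends to w′δ. Fitting a flat mean to a trend adds terms rr′ to the working covariance. Because w′r = 0 for each arm, the weights do not change. The 24-week difference, taken as the equal-weight mean of the six periods, is (1/6)Σδⱼ. The two agree if δ is constant (the weights sum to 1) or if the weights happen to balance.

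**4. Illustration. All inputs are assumed; none is in the documents.**

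- Control symptom mean falls linearly from 1.6 to 0.8 over six periods.
- δ = (0, -0.06, -0.12, -0.18, -0.24, -0.30). The true 24-week difference is -0.90/6 = -0.15.
- SD paths are linear. Correlation is compound-symmetric (CS) at 0.5 or 0.7, or AR(1) at 0.6 or 0.8.
- Data are complete, and the centre effect and covariates are ignored.

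| SD over the six periods | CS 0.5 | CS 0.7 | AR(1) 0.6 | AR(1) 0.8 |
|---|---|---|---|---|
| constant | -0.150 | -0.150 | -0.150 | -0.150 |
| 1.0 falling to 0.9 | -0.179 | -0.208 | -0.163 | -0.171 |
| 1.2 falling to 0.7 | -0.277 | -0.358 | -0.213 | -0.249 |
| 0.7 rising to 1.2 | -0.023 | +0.058 | -0.087 | -0.051 |

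Worked cell (CS 0.7, SD 1.2 to 0.7): the weights are (-0.211, -0.135, -0.022, 0.146, 0.405, 0.817). Then w′δ = 0 + 0.0081 + 0.0026 - 0.0263 - 0.0972 - 0.2451 = -0.358. This lies outside the range of the six true differences because the early weights are negative.

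If δ is set to -0.15 at every visit, all 16 cells return -0.150.

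**5. The 24-week estimate.** The MMRM code contains no `lsmeans rndgrp` and no averaged contrast. Taken literally, it asks for 4 endpoints × 6 visits = 24 p-values. SAP 5.5 applies no multiplicity adjustment, and nothing says which result tests the endpoint.

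**The case against.** **A 24-week analysis is nominally still planned.** The ANCOVA sentence in SAP 7.2.2, Protocol 9.4.2 and Protocol 9.3.2 together point to an ANCOVA of a mean of available diary values. This stands. A reader might infer that the plan holds no single estimate of the 24-week endpoint at all, and the documents do not support that. What they do show is that the SAP gives no derivation of a per-subject 24-week mean (its 14-day rule works at period level) and does not say whether the ANCOVA or the MMRM is the endpoint analysis. The table shells are in a separate file that is not available here, so they cannot settle the matter.

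**The model can return the right number.** This also stands. With a constant treatment effect, or with balancing weights as in the constant-SD row, it does. Saying that it can never give the 24-week difference would be too strong.

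**The figures depend on the assumptions.** Agreed. No document gives an SD path, a correlation or a visit profile of the effect. A reader who saw only the falling-SD rows might infer that the model exaggerates benefit; the rising-SD row shows the opposite. The weighting argument applies to PEF too, but no PEF figures are worked here.

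**The fault would show itself.** LSMEANS names an effect that is not in MODEL, so the code should fail visibly, and SAP 7.1.3 offers a complete model to copy. That makes the poor repair less likely, but the prose still specifies a model without visit, and the right repair would be a departure from it.

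**Equal weighting is a choice.** True. Visit windows of ±1 week make the periods unequal, so an average over available days is a different, also defensible, definition. The SAP has to pick one.

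**Conclusion.** The point holds as a specification error in SAP 7.2.2. By-visit LS means, differences and p-values are promised from a model whose mean has rank 2 across 12 treatment-by-visit cells. This needs no assumptions; it follows from the prose and code as written.

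The second part is conditional. The MMRM does not request the 24-week difference and does not in general give it. How far it misses, and in which direction, rests on assumed inputs: from no error to a result more than twice the true -0.15 (-0.36), or one near zero or of opposite sign (+0.06). An effect that varies over visits is plausible, since treatment in the ACT arm is adjusted at successive visits (Protocol 4.2), but the documents do not establish it.

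The reach is limited to four secondary endpoints. A reader might infer that the trial's main conclusion is at risk. It is not: the primary analysis uses a separate model for ACT response and is unchanged.

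**What to change.** In SAP 7.2.2, before database lock:

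1. Add visit and treatment-by-visit to the prose covariate list and to the code, as in SAP 7.1.3: `model endpoint = rndgrp visit rndgrp*visit actbl blcontrol gender age / ddfm=kr;`. The code already includes baseline ACT but the prose does not; align them in the same edit.
2. Name one 24-week estimate per diary endpoint, with its 95% CI and p-value. One option is the equally weighted average of the six visit differences: `estimate 'ACT vs UC, 24 weeks' rndgrp 6 -6 rndgrp*visit 1 1 1 1 1 1 -1 -1 -1 -1 -1 -1 / divisor=6 cl;` (check the level order). The other is an ANCOVA on a per-subject 24-week mean, with its derivation and minimum-data rule written out.
3. State that this is the endpoint analysis, that the by-visit differences are supportive, and how the general ANCOVA sentence relates to the MMRM. If the MMRM is the endpoint analysis, list it in SAP 2.1 as a change from Protocol 9.4.2.

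The cost is a few sentences and a few lines of code, with no new data and no change to trial conduct. The table shells need one added row or column per diary endpoint if they do not already have it.
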